2.3 Rationale for the Open-label Treatment Period

This OL treatment period is being conducted to evaluate the long-term safety, tolerability and efficacy of weekly IV doses of WVE-210201 over an additional 48 weeks. All patients who successfully complete the double-blind period of the study WVE-DMDX51-003 will receive treatment with WVE-210201 in the OL treatment period.

3 STUDY OBJECTIVES

3.1 Study Objectives-Double-blind Treatment Period

Primary Objectives

- To evaluate the efficacy of WVE-210201 by assessing changes in dystrophin levels (United States/Other regions as applicable)
- To evaluate the efficacy of WVE-210201 by assessing changes in motor function by North Star Ambulatory Assessment (NSAA) (EU/Japan)

Secondary Objectives

- To evaluate the efficacy of WVE-210201 by assessing changes in upper limb proximal strength
- To evaluate the efficacy of WVE-210201 by assessing changes in lower limb motor function
- To evaluate the efficacy of WVE-210201 by assessing changes in respiratory function
- To evaluate the efficacy of WVE-210201 by assessing changes in stride velocity
- To evaluate the safety of WVE-210201

Exploratory Objectives:

- To evaluate the efficacy of WVE-210201 by assessing changes in quality of life
- To assess the PK of WVE-210201 in plasma
- To evaluate the efficacy of WVE-210201 by assessing changes in upper limb function

- To evaluate the effect of WVE-210201 on dystrophin protein localization
- To evaluate the effect of WVE-210201 on exon-skipping
- To evaluate the efficacy of WVE-210201 by assessing changes in cardiac function (by echocardiogram [ECHO])
- To evaluate the efficacy of WVE-210201 by assessing changes in daily activity as measured by a wearable device
- To evaluate the efficacy of WVE-210201 by time to milestone events

3.2 Study Objective-Open-label Treatment Period

- To evaluate the long-term efficacy, safety and PK of WVE-210201

4 STUDY DESIGN

4.1 Study Design Overview

This is a Phase 2/3, multicenter, randomized, double-blind, placebo-controlled study with an OL extension, to evaluate the safety and efficacy of WVE-210201 in ambulatory male pediatric patients with DMD amenable to exon 51 skipping intervention.

The study will include a screening period (up to 6 weeks), a double-blind treatment period (48 weeks), an OL treatment period (48 weeks), and a safety follow-up.

4.1.1 Screening

Screening evaluations must be completed within 6 weeks of signing the informed consent form (ICF) and these assessments can occur on multiple days, provided they are within the Screening Period. The Investigator will determine whether patients meet eligibility criteria and will collect the demographic and medical data permitting full characterization of the patient. Patients who screen fail may be rescreened once.

A record of patient screen failures will be maintained for patients who do not qualify for enrollment, including the reason for the failure. A baseline open muscle biopsy (from deltoid) will be performed at least 2 weeks prior to the Day 1 visit. This will allow full recovery from the surgery prior to obtaining baseline functional assessments. All attempts should be made to complete all screening assessments and confirm patient eligibility for the study prior to muscle biopsy collection to prevent biopsies from being performed on patients not eligible for the study. The time from signing the ICF to Day 1, including screening and open muscle biopsy collection cannot exceed 6 weeks.

4.1.2 Double-blind Treatment Period

In the Double-blind Treatment Period, patients will receive weekly intravenous (IV) doses of either placebo or WVE-210201. Patients will be randomized in a 1:1:2:2 ratio to placebo 3 mg/kg, placebo 4.5 mg/kg, WVE-210201 3 mg/kg, and WVE-210201 4.5 mg/kg. Patients must be randomized within one day prior to their first dose. Safety and efficacy assessments will be performed over the course of study. All functional assessments, performance of upper limb (PUL), NSAA, myometry, timed function tests, and pulmonary function tests (peak flow rate [PFR], cough peak flow [CPF], and forced vital capacity [FVC]) and completion of the Pediatric Quality of Life questionnaires must be done pre-dose (on the dosing day or up to 24 hours prior to respective dosing day). The ActiMyo wearable device will also be given to patients, and activity data will be collected throughout the study at specified timepoints. To minimize the potential unblinding, functional assessments must be completed by an assessor not involved in administration of study drug or assessment and recording of AEs during the study. The same assessor should perform the functional assessments throughout the study for a given patient to minimize variability of assessments.

A second open muscle biopsy (deltoid) will be collected at 1 of 3 timepoints mentioned below:

- First 30 patients: Week 12
- Next 40 patients: Week 22
- Remaining patients: Week 46, 2 weeks prior to Week 48 visit.

The biopsy timing facilitates interim analyses of dystrophin; all biopsies will be used in the primary efficacy analysis. The open muscle biopsies will be collected to allow for adequate tissue quantity and quality for analysis of dystrophin-related study endpoints via Western blot analysis (dystrophin protein level), and other pharmacodynamic assessment methods (e.g., dystrophin localization by immunohistochemistry, exon skipping via RT-PCR).

In addition, pharmacokinetics of WVE-210201 will be determined. Immunogenicity analysis will also be performed.

Patients and parents will be asked to complete the quality of life questionnaires as applicable.

This Phase 2/3 study includes several planned interim efficacy analyses. Interim analyses of dystrophin will determine if efficacy is demonstrated prior to study conclusion and if adaptations to treatment arm allocation or clinical efficacy analyses are warranted. Interim analyses of the NSAA endpoint will determine if study enrollment can stop based on the predictive probability of success and will be performed at 4 pre-specified enrollment targets. Historical control datasets will be included in the computation of the predicted probability of success and the NSAA efficacy analysis. [Section 11.3.2](#) and [Section 11.5](#) include additional details on the interim analyses and the statistical methods planned.

After the Week 48 efficacy assessments are done pre-dose, all patients will transition to the OL treatment period and receive WVE-210201 (further details in [Section 4.1.2](#)).

The interim dystrophin analyses may serve to provide early evidence of efficacy as established by dystrophin production, which is the expected mechanism of action of WVE-210201. Positive evidence from these interim analyses may support early registration efforts in some regions in consideration of established regulatory policy where increased dystrophin protein levels are accepted as a surrogate endpoint reasonably likely to predict clinical benefit in support of accelerated approval. In the event that either interim dystrophin analysis results in a statistically significant finding in the dystrophin level in favor of WVE-210201, the study will continue and all patients will remain in the Double-blind Treatment Period (up to Week 48) to assess clinical outcomes and other endpoints. However, if a futility boundary is crossed at the second interim analysis, the study may be stopped due to lack of efficacy.

Japanese PK Cohort:

This is a global study that will include study sites in Japan. The PK of WVE-210201 in Japanese patients will be assessed in patients enrolled at clinical sites in Japan. The first 12 patients enrolled in Japan will be randomized in a 1:1:2:2 ratio to placebo 3 mg/kg, placebo 4.5 mg/kg, WVE-210201 3 mg/kg, and WVE-210201 4.5 mg/kg and undergo intensive PK sampling. After the first dose of study drug (WVE-210201 or placebo), Japanese patients in the PK cohort will remain in the clinic for a period of at least 24 hours or longer, based on the Investigator's judgement.

Enrollment of additional patients at Japanese clinical sites will not occur until the 12 patients have completed at least 2 weeks of follow-up, the PK and safety data have been reviewed, and a decision has been made to proceed. The Sponsor will be blinded to the results of these analyses. Patients will be replaced if they drop out before 2 weeks of follow-up.

Except for the intensive PK sampling and additional safety monitoring in the 24-hour period following the first dose of WVE-210201, the schedule of events for the Japanese PK cohort will be the same as for patients not enrolled at Japanese clinical sites, including the biopsy procedures.

Stopping Criteria for Japanese PK Cohort

The Phase 1 study of WVE-210201 did not include patients of Japanese descent. As such, this is the first time Japanese patients will receive WVE-210201 and stopping criteria for the Japanese PK cohort have been established. If any of the stopping criteria, as defined below, are met in the Japanese PK cohort, dosing will be suspended for patients in the Japanese PK cohort and the data will be reviewed by the unblinded Data Monitoring Committee (DMC) to determine whether it is safe to proceed with dosing in the cohort.

- If a single patient experiences a serious AE assessed as related to treatment
- If 2 or more patients experience a treatment emergent adverse event (TEAE) graded by the investigator as "severe" in intensity and assessed as related to treatment.

If a determination is made to resume dosing in the Japanese PK cohort following the review of safety data related to any event(s) that meet the stopping criteria, information will be submitted to the applicable regulatory authorities (in Japan) in accordance with local regulations prior to restarting treatment. If a decision is made to terminate dosing in the Japanese PK cohort, all Investigators in Japan will be informed immediately.

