4.3 Study Endpoints

4.3.1 Double-blind Treatment Period

Study Endpoints: The primary and key secondary efficacy endpoints differ by region. All other endpoints are the same across regions.

Primary Efficacy Endpoint

- Change from baseline in dystrophin level (% normal dystrophin) assessed by Western blot of muscle tissue (United States/Other regions, as applicable)
- Change from baseline in North Star Ambulatory Assessment (NSAA) through 48 weeks (EU/Japan)

Secondary Efficacy Endpoints

- Key secondary endpoint - Change from baseline in NSAA through 48 weeks (United States/Other regions, as applicable)
- Key secondary endpoint - Change from baseline dystrophin level (% normal dystrophin) assessed by Western blot of muscle tissue (EU/Japan)
- Change from baseline in upper limb proximal strength assessed by hand held myometry through 48 weeks
- Change from baseline in 4-stair climb (4SC) through 48 weeks
- Change from baseline in the 10-meter walk/run test through 48 weeks

- Change from baseline in forced vital capacity (FVC; % predicted) through 48 weeks
- Change from baseline in the 95th percentile of stride velocity through 48 weeks

Exploratory Efficacy Endpoints

- Change from baseline in Pediatric Quality of Life Inventory (PedsQLTM)-neuromuscular module at 48 weeks
- Change from baseline in Pediatric Quality of Life Inventory (PedsQLTM)-Generic Core Scale module at 48 weeks
- Change from baseline in individual NSAA items through 48 weeks
- Change from baseline in respiratory function (peak flow rate [PFR], cough peak flow [CPF]) through 48 weeks
- Change from baseline in PUL 2.0 through 48 weeks
- Time to milestone events (loss of ambulation, loss of self-feeding, requirement of daytime ventilation on a regular basis)
- Changes from baseline in daily activity as measured by a wearable device measure

Safety, Pharmacokinetic and Pharmacodynamic Endpoints

- Adverse events, laboratory values, physical exams and vital signs
- Changes from baseline in cardiac functions by ECHO
- Concentration of WVE-210201 in plasma
- Concentration of WVE-210201 in muscle
- Exon-skipping by RT-PCR in muscle tissue
- Dystrophin localization by immunofluorescence

4.3.2 *Open-label Treatment Period*

- Long-term efficacy, safety, and PK of WVE-210201

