11 STATISTICAL METHODS

11.1 Sample Size Determination

Approximately 150 patients are planned to be enrolled in this study. This study was designed to demonstrate the efficacy of WVE-210201 compared to placebo on a clinical endpoint, NSAA.

The sample size determination for the NSAA endpoint was based on the following assumptions:

- Two-sample t-test to test for statistical significance of treatment difference

- 1:1:2:2 placebo 3 mg/kg, placebo 4.5 mg/kg, WVE-210201 3 mg/kg, and WVE-210201 4.5 mg/kg randomization ratio
- Standard deviation of change in NSAA from baseline to 48 weeks⁵⁵ of 4.5
- Treatment difference of change in NSAA from baseline to 48 weeks of 3.0 between WVE-210201 and placebo
- Dropout rate of 10%
- Two-sided significance level of 5%

With these assumptions, a sample size of 150 patients provides 88% power to detect a difference of 3 in the change in NSAA from baseline to 48 weeks. The treatment difference of 3 was selected as it is equal to the average 1-year decline observed in longitudinal natural history studies^{55,56}.

The power of the dystrophin endpoint was based on the following assumptions:

- Two-sample t-test to test for statistical significance of treatment difference
- 150 patients randomized 1:1:2:2 placebo 3 mg/kg, placebo 4.5 mg/kg, WVE-210201 3 mg/kg, and WVE-210201 4.5 mg/kg
- Standard deviation of change in dystrophin protein level from baseline to 46 weeks of 3.0%
- Treatment difference of change in dystrophin protein level from baseline to 46 weeks of 4.0% between WVE 210201 and placebo
- Dropout rate of 10%
- Two-sided significance level of 5%

With these assumptions, the power is greater than 99% to detect a difference of 4% in the change in dystrophin level from baseline to 46 weeks.

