11.3.2 Analyses of Efficacy Endpoints

11.3.2.1 Analysis of dystrophin protein level

A primary objective of this Phase 2/3 study is to evaluate the efficacy of WVE-210201 by assessing changes in dystrophin protein levels. Therefore, the primary efficacy endpoint for the United States and Other regions, as applicable, and the key secondary endpoint for the EU and Japan is the change in dystrophin protein level (% normal) from baseline. The treatment policy estimand, which assesses the effect of treatment initially assigned at baseline (regardless of adherence to the planned course of treatment), will be used. The analysis population will be the ITT population. The main estimator is a Bayesian analysis of covariance (ANCOVA). The model will include fixed effects for mean change from baseline in dystrophin levels at each time point for placebo and fixed effects for the increase or decrease in dystrophin compared to placebo for each treatment arm at each time point.

Let the change from baseline in dystrophin level at time point j for patient i be Y_{ij} , for $j = 1, 2, 3$ and $i = 1, \dots, n$. Time periods $j = 1, 2$, and 3 , refer to the post-baseline visits at 12, 22 and 46 weeks; each patient will have one Y_{ij} with either $j = 1, 2$, or 3 . The ANCOVA model is

$$Y_{ij} = \alpha_j + \theta_{t(i),j} + \epsilon_{ij};$$

$$\epsilon_{ij} \sim N(0, \sigma_{t(i),j}^2).$$

The $\alpha_j, j = 1, 2, 3$, parameters represent the mean change from baseline in dystrophin level at each time point for placebo-treated patients. For patient i , the treatment arm is labelled $t(i)$ with 0 for placebo, 1 for WVE-210201 3 mg/kg and 2 for WVE-210201 4.5 mg/kg. The effect of treatment T at time j is the parameter $\theta_{T,j}, T = 0, 1, 2$ and $j = 1, 2, 3$. For placebo, the effect is assumed to be 0 ($\theta_{0,j} = 0$). Thus, the treatment effect parameter for treatment T at time j represents the mean difference in the change from baseline in dystrophin at time j compared to placebo. The errors for the individual observations, ϵ_{ij} , are assumed independent and follow a normal distribution. The standard deviation, $\sigma_{T,j}, T = 0, 1, 2$ and $j = 1, 2, 3$, is specific to treatment arm and visit.

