With this plan, the 12-week WVE-210201 4.5 mg/kg treatment effect is assessed at the first dystrophin interim analysis, the 22-week WVE-210201 4.5 mg/kg treatment effect is tested at the second dystrophin interim analysis and the 46-week WVE-210201 4.5 mg/kg treatment effect is tested at the final dystrophin interim analysis. Similar comparisons will be made for the WVE-210201 3 mg/kg treatment effect if the 4.5 mg/kg treatment effect is significant.

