11.5.1 Dystrophin Interim Analyses

Interim analyses of dystrophin will determine if efficacy is demonstrated prior to study conclusion and may allow for stopping randomization to the WVE-210201 3 mg/kg arm. The

first interim dystrophin analysis will compare dystrophin protein levels between WVE-210201 and placebo using the Week 12 open biopsies collected from up to the first 30 patients randomized. The second interim dystrophin analysis will compare dystrophin protein levels between WVE-210201 and placebo from approximately 40 patients with Week 22 open biopsies (collected from the 31st through 70th patient). The dystrophin interim analyses will be supplemented with dystrophin data from the ongoing OL extension study to the Phase 1 trial (WVE-DMDX51-002). A final analysis of dystrophin will occur when up to 80 patients (collected from the 71st through a maximum of the 150th patient) have Week 46 open biopsies. The significance thresholds for the dystrophin analyses are described in [Section 11.3.2.1](#). If the first or second interim dystrophin analysis results in a significant WVE-210201 treatment effect, randomized patients will continue to complete 48 weeks of follow-up to assess clinical outcomes and other endpoints.

Randomization to the WVE-210201 3 mg/kg treatment arm may be stopped based on the interim analysis of dystrophin. Specifically, randomization to the WVE-210201 3 mg/kg treatment arm will stop, if there is a high posterior probability that the high dose is effective, and the low dose is less efficacious of the high dose. The specific thresholds are included in the SAP.

If randomization to the 3 mg/kg treatment arm is stopped, patients originally randomized to the 3 mg/kg treatment arm will be transitioned to the WVE-210201 4.5 mg/kg treatment arm and all future patients will be randomized to WVE-210201 4.5 mg/kg or placebo at a 2:1 ratio. For clinical endpoint analyses, including the NSAA, patients originally randomized to the WVE-210201 3 mg/kg arm who transition to the WVE-210201 4.5 mg/kg treatment arm will not be included in WVE-210201 4.5 mg/kg treatment effect estimation.

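### Dystrophin data base and power are stated for all biopsies and all 150 patients, but the final test rests on the Week 46 cohort of at most 80

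*Combined protocol and SAP*

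**What the plan says.** Section 4.1.2 and the synopsis schedule one second biopsy per patient: "First 30 patients: Week 12", "Next 40 patients: Week 22", and Week 46 for the rest. They then state: "The biopsy timing facilitates interim analyses of dystrophin; all biopsies will be used in the primary efficacy analysis".

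Section 4.3.1 names no time point for the endpoint: "Change from baseline in dystrophin level (% normal dystrophin) assessed by Western blot of muscle tissue (United States/Other regions, as applicable").

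Section 11.1 bases power on 150 patients, SD 3.0%, 10% dropout, a two-sample t-test at two-sided 5%, and: "Treatment difference of change in dystrophin protein level from baseline to 46 weeks of 4.0% between WVE 210201 and placebo". It reports power above 99%.

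Section 11.3.2.1 fits a Bayesian ANCOVA in which the time periods "refer to the post-baseline visits at 12, 22 and 46 weeks; each patient will have one" outcome. The placebo mean, the treatment effect and the SD are each specific to the week. Success for 4.5 mg/kg requires a posterior probability above 1 - 0.025/3 = 0.991667 for the Week 12 effect at the first interim, the Week 22 effect at the second, or the Week 46 effect at the final analysis; 3 mg/kg is tested only after 4.5 mg/kg succeeds. For the last look: "the 46-week WVE-210201 4.5 mg/kg treatment effect is tested at the final dystrophin interim analysis".

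Section 11.5.1 gives the cohort for that look: "A final analysis of dystrophin will occur when up to 80 patients (collected from the 71st through a maximum of the 150th patient").

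**The concern.** A reader of Section 4.1.2 would expect the early biopsies to serve twice: at their interim look and again in the final primary result. A reader of Section 11.1 would expect 150 patients to have a 46-week value. The design supports neither expectation. At most 80 patients have a Week 46 biopsy, and in the model as written nothing carries Week 12 or Week 22 information to the 46-week effect.

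At stake is the evidence base described for an endpoint that, according to the protocol, may support accelerated approval. The exposure to early stopping is also hidden. The NSAA interim analyses in Section 11.5.2 can end enrollment below 150, and every patient lost that way comes out of the Week 46 dystrophin cohort once 70 have been randomized.

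**Working it through.** **Inputs.** Section 11.1: N = 150, 1:1:2:2 allocation, difference 4.0%, SD 3.0%, dropout 10%, two-sided 5%. Sections 4.1.2 and 11.5.1: cohorts of 30, 40 and up to 80. Section 11.3.2.1: one-sided level 0.025/3 = 0.00833 per look, 4.5 mg/kg first, one placebo group in the model. Pooling the two placebo arms makes the allocation 1:1:1.

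**Formulas.** SE = SD x sqrt(1/n1 + 1/n2). Power comes from the noncentral t with noncentrality difference/SE. This is a frequentist stand-in for the posterior-probability rule, because the text gives no priors.

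**1. The plan's own figure.** 150 x 0.9 = 135, or 45 per group. For 45 v 45, SE = 3 x sqrt(2/45) = 0.63 and 4/0.63 = 6.3. Power at two-sided 5% exceeds 99.99%. Pooling the doses (45 v 90) also exceeds 99.99%. The stated figure reproduces, but only by crediting all 150 patients with a 46-week value.

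**2. The final test as specified.** 80/3 = 26.7 per group, and 26.7 x 0.9 = 24. SE = 3 x sqrt(2/24) = 0.87 and 4/0.866 = 4.62.
- Normal approximation: Phi(4.62 - 2.39) = 98.7%.
- t-test: 98.1%. With no dropout (26.7 v 26.7) it is 99.0%.
- Rough check with dropouts set to zero change, close to the baseline imputation in Section 11.3.2.1: effect 0.9 x 4 = 3.6; variances 0.9 x 9 + 0.09 x 16 = 9.54 (active) and 0.9 x 9 = 8.1 (placebo); SE = sqrt((9.54 + 8.1)/26.7) = 0.81; power about 97.9%.

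**3. Across the three looks.** The cohorts are different patients, so the tests combine as independent. Group sizes after dropout are 9, 12 and 24.

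| Assumed true effect at Weeks 12 / 22 / 46 | Week 12 | Week 22 | Week 46 | At least one |
|---|---|---|---|---|
| 4 / 4 / 4% | 57% | 74% | 98.1% | 99.8% |
| Linear accrual: 1.04 / 1.91 / 4% | 4% | 18% | 98.1% | 98.5% |

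Linear accrual means 4 x 12/46 = 1.04 and 4 x 22/46 = 1.91. The last column is 1 minus the product of the three failure probabilities. Under the null it is 1 - (1 - 0.00833)^3 = 0.0248, within 0.025.

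**4. Early enrollment stop** (totals assumed; no arm dropped). Per-group n is (N - 70)/3 x 0.9.

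| Total N | Week 46 cohort | n per group | Final-test power for 4% |
|---|---|---|---|
| 150 | 80 | 24 | 98% |
| 130 | 60 | 18 | 92% |
| 110 | 40 | 12 | 74% |
| 100 | 30 | 9 | 57% |

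**5. If the 3 mg/kg arm stops before patient 71.** All 80 are randomized 2:1, giving 24 v 48 after dropout and power of 99.8%. The adaptations therefore move the contrast in both directions.

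**6. Smaller true effects** (assumed). At 3%, final-test power is 83% (24 v 24, one-sided 0.00833), against 99.7% on the Section 11.1 basis (45 v 45, two-sided 5%). At 2% it is 44% against 88%.

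**The case against.** The strongest reply is that the plan has one explicit rule. Section 4.1.2 refers the reader to Sections 11.3.2 and 11.5, which say which week is tested at each look, in what dose order and at what threshold. One model covers all three cohorts, every cohort feeds one test that can win the primary claim, and effects with credible intervals are reported for every week. Used need not mean pooled. Section 4.3.1 is incomplete rather than contradictory, and Section 11.1 states a power assumption, not an endpoint. Separate cohorts with a Bonferroni split are a legitimate design.

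Most of this stands. A reader might infer that the protocol holds three competing primary endpoints; it does not, because Section 11.3.2.1 settles what is tested. A reader might also infer that the final result rests on only 53 of 150 patients. That sets a two-arm count against a three-arm total. Like for like it is up to 80 of 150, or about 53 of 100 in the 4.5 mg/kg and placebo arms, and either adaptation changes the count. Nor do the documents require a pooled all-biopsy estimate: its meaning is unclear when the effect may differ by week, and its weights would depend on when enrollment stops.

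Two limits apply to the calculation. Section 11.3.2.1 supplements the dystrophin analysis with data from the open-label extension study, and priors are not given; neither is modeled here. A prior could in principle link the weeks, but the text describes fixed effects and states no link.

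The reply does not answer the power basis. Section 11.1 uses 150 patients at two-sided 5%, whereas at most 80 have the outcome and each look is tested at one-sided 0.00833.

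**Conclusion.** The point holds as a mismatch between what is stated and what is tested. The all-biopsies sentence and the Section 11.1 power basis describe more data than the final dystrophin test has. On the plan's own inputs the loss is small: from above 99.99% on the Section 11.1 basis to about 98% at the final look, just under the stated figure. Across the three looks, power is about 98.5% under linear accrual and 99.8% if 4% already holds at Weeks 12 and 22; both patterns are assumptions. The SE of the final contrast is 0.87 points, against the 0.63 implied by Section 11.1.

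The mismatch becomes material if enrollment stops early or the true effect is well below 4%. It would be wrong to conclude that the planned effect is at risk at full enrollment, or that type I error is affected. The figures assume SD 3% in every arm and week, 10% dropout, no arm dropped unless stated, and no borrowing from the extension study.

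**What to change.** - **Section 4.3.1 (and the synopsis endpoint list):** name the time point as the biopsy week tested at each look (12, 22, 46), with Week 46 at the final analysis.
- **Synopsis and Section 4.1.2:** replace the all-biopsies sentence. Say that each biopsy enters the test for its own week, and that the final test uses only the Week 46 cohort, whose size depends on the arm-dropping and enrollment-stopping rules. Do not fix a per-arm number there.
- **Section 11.1 (and the synopsis):** restate dystrophin power for 4.5 mg/kg v placebo at one-sided 0.025/3. Give about 98% at the final look, about 98.5% across looks under linear accrual, 99.8% if 4% holds from Week 12, and the lower values under an early enrollment stop, with the assumptions labeled.
- **Optional:** a weighted average over all biopsies, pre-specified as supportive only.

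The cost is wording and one restated power paragraph. Model, thresholds and type I error are unchanged. The downside is a slightly less favorable stated power and data base.
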